### Description of the Study Design

If you agree to participate in this research study, the following information describes what may be involved.

Your study involvement will begin on the day of your surgery at Mount Sinai Hospital. Prior to starting surgery, you will undergo two regional anesthesia blocks. You will receive an intravenous medication called midazolam to reduce anxiety and help tolerate the procedures. One of them is called the adductor canal block, which is typically performed for your surgery regardless of the research study. An ultrasound will be used to identify the location of nerves in your upper leg, and a numbing medication called bupivacaine will be injected around the identified area. The other is called the obturator nerve block, which is being evaluated in this research study. Once again, an ultrasound will be used to identify the location of nerves in your upper leg close to the groin area, which will be appropriately draped. Once this area is identified, a solution will be injected which is either bupivacaine or saline that does not contain any active medication. Once these procedures are completed, the rest of the anesthesia for the surgery will proceed the same as if you are not part of the research study. This includes a spinal anesthesia that will make the lower part of your body numb, and any sedation given by the anesthesiologist to help you feel relaxed and comfortable enough to tolerate the surgery.

After your surgery, you will be taken to a surgery recovery area before you are able to go to your own hospital room. There, you will be given a button to push to receive an intravenous opioid medication. You will have the freedom to decide when to receive the medication but it will be set up so that you cannot receive more than your doctors intended. You will also have nausea medications available. The study doctor will ask you about your pain level and nausea level. The doctor will also review how much opioid medication you received by pushing the button.

You will periodically be asked questions regarding your pain and nausea and vomiting during the rest of your hospital stay. Your performance during your physical rehabilitation sessions will also be reviewed by study doctors.

At your first postoperative visit with your surgeon after your discharge from the hospital, you will be asked about your pain levels after your discharge and your overall satisfaction with your pain control.

The study treatment you get will be chosen by chance, like flipping a coin. Neither you nor the study doctor will choose what study treatment you get. You will have an equal chance of being given each

study treatment. Neither you nor the study doctor will know which study treatment you are getting. This information could be obtained in an emergency, however.

#### Description of Procedures Being Performed

Subjects who consent to and are scheduled for total knee arthroplasty under regional anesthesia will be invited to participate in the study during a routine preoperative visit prior to surgery. The details of the study will be reviewed and written informed consent will be obtained.

The patient will be randomized into the study group or the placebo group. On the day of surgery, the group allocation will be revealed to an anesthesiologist not part of the research study, who will receive specific instructions to prepare an injectate solution for the obturator nerve block, which will consist of 0.25% bupivacaine for the study group or saline for the placebo group.

The patient will receive midazolam for anxiolysis at the discretion of the attending anesthesiologist. An adductor canal block with 10mL 0.25% bupivacaine will be performed. An obturator nerve block will be performed with the previously prepared injectate solution. Patients will undergo spinal anesthesia with a 3mL solution of 0.75% bupivacaine. Sedation may be administered during surgery at the discretion of the anesthesiologist.

Total knee arthroplasty will be performed by the orthopedic surgeon with insertion of bicompartmental or tricompartmental prostheses using a standard medial parapatellar approach and hand-mixed cementing techniques. A local intraarticular injection will be performed intraoperatively by the surgeon, as is routinely done for total knee arthroplasties by the surgeon involved in our study, regardless of research involvement.

In the Post Anesthesia Care Unit, the patient will be administered hydromorphone using intravenous patient-controlled analgesia (PCA). Fentanyl will be administered if hydromorphone is not tolerated. Additional oral oxycodone consumption will also be recorded.

Relevant preoperative, intraoperative, and postoperative data will be obtained from the anesthesia record, the EPIC electronic medical record. The patient will also be interviewed by study personnel at time of first post-discharge follow-up visit to obtain analgesia satisfaction scores.

#### Description of instruments created by research team

The data collection sheet created by the research team will be used to gather preoperative, intraoperative, and postoperative data relevant to the study. Preoperative data to be collected includes patient demographics including age and gender. Intraoperative data include duration of surgery, total narcotics administered during surgery, and total fluids administered. Postoperative data include total narcotics administered, pain scores at regular various intervals, incidence of postoperative nausea and vomiting, and time to ambulation. Data will also be extracted from the patient's first completed physical therapy session, including total distance ambulated, pain at time of assessment, and functional mobility impairment percentage. Post-discharge data to be collected include total dosage of narcotics used after discharge, pain score, and any complications.

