## Background

The management of postoperative pain after total knee arthroplasties remains a challenging issue. Even though postoperative pain typically ranges from moderate to severe, patients are encouraged and expected to start physical therapy and ambulate as soon as possible because early rehabilitation may lead to improved long-term functional status of the knee. Integrated multimodal analgesic strategies have been employed for postoperative pain management; the aim of such strategies is to utilize different mechanisms of action to provide superior analgesia while limiting side effects and adverse events. Multimodal analgesic strategies for total knee arthroplasties most commonly combine regional anesthesia techniques, including femoral nerve block and local infiltration analgesia, with a combination of low-dose opioids, acetaminophen, and nonsteroidal anti-inflammatory drugs.

The optimal peripheral nerve block or combination of blocks is not yet known. Since the knee joint is innervated by an anterior and posterior group of sensory nerves, an approach that provides regional anesthesia to both groups seem reasonable. The femoral nerve block provides analgesia of the knee in the anteromedial region. However, despite the improved analgesia and shortened hospital stays provided by the use of femoral nerve blocks in total knee arthroplasties, the motor weakness that can be caused by these regional blocks can delay mobilization and increase the risk of falls.

Recently, the adductor canal block has become more frequently used because of claims that femoral nerve block can increase fall risk. The adductor canal block blocks the saphenous nerve and is primarily a sensory block, even though it can result in the partial motor block of the vastus medialis muscle. Overall, the adductor canal block has exhibited relative spring of quadriceps strength and was shown to be not inferior in providing analgesia and opioid consumption.

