The obturator nerve block has also been utilized for total knee arthroplasties. The obturator nerve provides innervation to the posterior group of sensory nerves. The femoral nerve block has not been shown to provide consistent block of the obturator nerve, and the addition of sciatic nerve block to a femoral nerve block does not further improve analgesia of the posterior knee. However, the addition of the obturator nerve block to a femoral nerve block has been shown to improve postoperative analgesia after total knee arthroplasty. The addition of obturator nerve block to femoral triangle block has also been shown to reduce opioid consumption without impairing ambulation.

Based on the above studies, various multimodal analgesic strategies, including various combinations of regional anesthetic techniques, have been utilized, with varying success. There is no consensus on the optimal strategy that provides the most effective postoperative analgesia while preserving ambulation and limiting side effects such as nausea and vomiting. We believe that the obturator nerve block in addition to adductor canal block and local infiltration analgesia can target both the anterior and posterior distribution of nerves to the knee to provide superior analgesia while not limiting ambulation. To date, we are not aware of any studies that have examined this particular combination of regional anesthetic techniques.

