#### Secondary objectives:

- f. Measure the severity of pain at rest using an 11-point Likert scale at 1, 6, 12, 24 hour marks postoperatively in patients who receive adductor canal block, obturator nerve block, and local infiltration analgesia versus patients who receive adductor canal block and local infiltration analgesia
- g. Compare time to breakthrough pain after surgery in patients who receive adductor canal block, obturator nerve block, and local infiltration analgesia versus patients who receive adductor canal block and local infiltration

- h. Measure rate of post-operative nausea/vomiting in patients who receive adductor canal block, obturator nerve block, and local infiltration analgesia versus patients who receive adductor canal block and local infiltration
- i. Measure time to ambulation in patients who receive adductor canal block, obturator nerve block, and local infiltration analgesia versus patients who receive adductor canal block and local infiltration
- j. Compare analgesia satisfaction score at time of first postoperative follow-up visit in patients who receive adductor canal block, obturator nerve block, and local infiltration analgesia versus patients who receive adductor canal block and local infiltration.

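### The data sheet lists complications only after discharge and never lists falls or block-related events, so an in-hospital harm of the preoperative block has no named field

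*Protocol*

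**What the plan says.** The protocol section on instruments created by the research team sets out the data sheet by period. For the hospital stay it says: "Postoperative data include total narcotics administered, pain scores at regular various intervals, incidence of postoperative nausea and vomiting, and time to ambulation". It then adds data from the first completed physical therapy session, "including total distance ambulated, pain at time of assessment, and functional mobility impairment percentage". For the period after discharge it says: "Post-discharge data to be collected include total dosage of narcotics used after discharge, pain score, and any complications". That last sentence is the only one with a complications item.

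The Description of the Study Design places the intervention before the operation: "Prior to starting surgery, you will undergo two regional anesthesia blocks". The obturator injectate is bupivacaine or saline, and the adductor canal block is given to both arms. The same section tells patients: "Your performance during your physical rehabilitation sessions will also be reviewed by study doctors".

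Time to ambulation is a secondary objective ("Measure time to ambulation in patients who receive adductor canal block, obturator nerve block, and local infiltration analgesia", against the control arm). Falls appear in the Background, where it is said of femoral nerve block that "the motor weakness that can be caused by these regional blocks can delay mobilization and increase the risk of falls". The Background closes with the belief that the added obturator block will give superior analgesia with no loss of ambulation. The SAP gives general tests for categorical and continuous variables and names no safety outcome.

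**The concern.** The randomised exposure is one preoperative injection, with no catheter or repeat dose described. If it causes a fall, a leg giving way or a local complication, the hospital stay is the first place to look. That is the period for which the data sheet lists no complications item.

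Two things are at stake. First, time to ambulation cannot stand in for safety: it rewards early walking and does not register what happens next. Second, a report that the added block improved analgesia and preserved ambulation would have no systematically collected, by-arm count of in-hospital falls or block complications beside it. Such an event would reach the dataset only if someone chose to note it, or if it was still present or recalled at follow-up. The trial is blinded and placebo-controlled, so a common field completed in both arms would give a fair comparison at almost no cost.

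**Working it through.** The plan gives no figure to reproduce here: no sample size, effect size, event rate, block duration or length of stay is stated. The check is a comparison of sections, followed by an illustration of what counts could show.

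**Step 1. What is listed, by period** (data-sheet section)

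| Item | In hospital | After discharge |
|---|---|---|
| Opioid use | listed | listed |
| Pain score | listed | listed |
| Nausea and vomiting | listed | not listed |
| Time to ambulation | listed | not applicable |
| Distance, pain and mobility impairment at first completed therapy session | listed | not applicable |
| Complications (general) | not listed | listed |
| Falls, near-falls, leg giving way | not listed | not listed by name |
| Block-related events | not listed | not listed by name |

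The available objectives and the SAP add nothing to the three lower rows.

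**Step 2. Do the in-hospital items cover the gap?** Nausea and vomiting is a harm, but mainly one of opioids. Time to ambulation is fixed once the patient first walks, so a later fall cannot change it. Distance and impairment percentage could reflect a weak leg, but they describe function at one session and are not event records. They also come from the first *completed* session, so a session abandoned because the leg gave way need not contribute. The rehabilitation review has no listed output beyond these items.

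**Step 3. What could counts show?** All inputs below are assumptions except the SAP's alpha of 0.05 and beta of 0.2; a two-sided test and 1:1 allocation are assumed.

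Illustrative arm sizes, for a difference in means with standardised effect d: n per arm = 2 × (1.960 + 0.842)² / d² = 15.70 / d², rounded up.
- d = 0.8: 15.70 / 0.64 = 24.5, so 25
- d = 0.5: 15.70 / 0.25 = 62.8, so 63
- d = 0.3: 15.70 / 0.09 = 174.4, so 175

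One-sided 95% upper bound on the rate when no event is seen: 1 − 0.05^(1/n). Chance of at least one event when the true risk is p: 1 − (1 − p)^n.

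| n | Upper bound, zero events | P(≥1), p = 1% | P(≥1), p = 2% | P(≥1), p = 5% |
|---|---|---|---|---|
| 25 | 11.3% | 22% | 40% | 72% |
| 50 | 5.8% | 40% | 64% | 92% |
| 63 | 4.6% | 47% | 72% | 96% |
| 175 | 1.7% | 83% | 97% | >99% |

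The rule of three gives 3/50 = 6% at n = 50, in line with the exact 5.8%. At the smaller sizes the trial could easily see no fall at all, and seeing none would leave a rate of several percent open. The counts are descriptive safety information, not a test.

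**The case against.** The strongest reply is that little is missing. Opioid use in the PACU is the research question. Weakness and falls are raised in the Background against femoral block, to explain the move to adductor canal block, which both arms receive. For the obturator block the Background cites a favourable study: "The addition of obturator nerve block to femoral triangle block has also been shown to reduce opioid consumption without impairing ambulation". Mobility is measured in hospital in several ways, and study doctors review rehabilitation. The data-sheet sentences say the data include these items, which need not be exhaustive, and postoperative data come from the electronic record, where a fall might be noted anyway. Some protocol sections were not available for this review and may cover risks or event reporting. Any counts would be too small to test.

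Much of this stands, and it rules out stronger readings that a reader might infer:
- That falls are the harm that motivates the trial. They are not; analgesia and opioid use are, with preserved ambulation as a condition.
- That harm is observed in the wrong window altogether. It is not; nausea and vomiting and mobility are collected in hospital.
- That block-related weakness and falls occur mainly in hospital and are over by discharge. The documents give no block duration, length of stay or timing of falls.
- That the plan as a whole has no in-hospital event reporting. This cannot be asserted from the text available.

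What does not stand is the inference that the gap is closed. The cited study concerns ambulation, with a different companion block, and does not establish the fall risk of this combination. An event that may sit in the chart is not the same as a field completed for every patient in both arms.

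**Conclusion.** The point holds in a limited form, as a cheap improvement to data collection. The data-sheet list names complications only after discharge and names neither falls nor block-related events, while the randomised injection is given before surgery. The mobility and nausea items collected in hospital do not record those events.

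The gap amounts to a few fields, and neither the primary comparison nor any planned test is affected. What is lost is a by-arm safety count to read beside time to ambulation, and that count could only bound a rate.

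This rests on reading the data-sheet list as the working collection form, and on the assumption that some block-related harm can arise before discharge. The sample sizes and event risks used for scale are illustrative.

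**What to change.** In the data-sheet section:
1. Run the general complications item from block placement through discharge, and keep it after discharge.
2. Add in-hospital falls, near-falls (including knee or leg giving way during therapy, whether or not the session was completed) and block-related events, each with date and time, and a yes/no entry for every patient so that a blank is not read as none.
3. Name the sources: the electronic medical record and the therapy notes already under review, abstracted blind to allocation.

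In the SAP, add one sentence: counts and proportions of these events by arm, with exact confidence intervals, reported descriptively beside time to ambulation and without a claim of equivalence. If event reporting is already defined elsewhere in the protocol, a cross-reference from the data sheet and the SAP sentence may be enough.

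The cost is slightly more data entry, with no new visit, procedure or change of treatment. The drawback is that counts will be low, so the report must say that few or no events does not show the block to be safe.

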#### Where and when consent will be obtained

Patients will be introduced to the study in the surgeon's office at [name] offices for the Department of Orthopedics (FPA). Patient will be informed about the study in more detail via telephone call prior to surgery. Official written consent will be obtained in the preoperative assessment area at Mount Sinai Hospital on the day of surgery.

#### Waiting period for obtaining consent

Official written consent will be obtained on the day of surgery. Patients will be given anywhere from 3 days to 2 weeks from when they are first introduced to the study until time of obtaining consent.

Protocol Title: Evaluating the addition of obturator nerve block to adductor canal block for total knee arthroplasty

Statistical Analysis Plan

PI: [name]

NCT03326999

Date: Sept 29, 2017

Prior to the beginning of the study, a sample size calculation was performed and was based on an  $\alpha$  of 0.05 and a  $\beta$  of 0.2. Patients were randomized into an intervention and control group. Baseline characteristics of subjects in each group were compared using chi-square tests for categorical variables and independent t-tests for continuous variables. No significant differences were detected between the baseline characteristics of each group; thus, direct comparisons of the outcomes of each group were analyzed. For categorical variables, chi-square tests were utilized, unless one value in the 2x2 matrix was under 5, in which case Fischer's exact test was utilized. For binary tests, odds ratios with 95% confidence intervals were reported. For continuous variables, independent t-test was used. All calculations were performed via SAS Statistical Software (Cary, NC).

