Protocol Title: Evaluating the addition of obturator nerve block to adductor canal block for total knee arthroplasty

PI: [name]

NCT03326999

Date: Sept 29, 2017

Protocol Title: Evaluating the addition of obturator nerve block to adductor canal block for total knee arthroplasty

Research Question: Does the addition of obturator nerve block to a regional anesthesia technique with adductor canal block and local infiltration analgesia for total knee replacement surgery reduce opioid consumption in the PACU?

Primary objective: Compare the rate of IV opioid consumption in patients who receive a combination of adductor canal block, obturator nerve block, and local infiltration analgesia at the surgical site versus patients who receive adductor canal block and local infiltration analgesia.

Secondary objectives:

- a. Measure the severity of pain at rest using an 11-point Likert scale at 1, 6, 12, 24 hour marks postoperatively in patients who receive adductor canal block, obturator nerve block, and local infiltration analgesia versus patients who receive adductor canal block and local infiltration analgesia
- b. Compare time to breakthrough pain after surgery in patients who receive adductor canal block, obturator nerve block, and local infiltration analgesia versus patients who receive adductor canal block and local infiltration
- c. Measure rate of post-operative nausea/vomiting in patients who receive adductor canal block, obturator nerve block, and local infiltration analgesia versus patients who receive adductor canal block and local infiltration
- d. Measure time to ambulation in patients who receive adductor canal block, obturator nerve block, and local infiltration analgesia versus patients who receive adductor canal block and local infiltration
- e. Compare analgesia satisfaction score at time of first postoperative followup visit in patients who receive adductor canal block, obturator nerve block, and local infiltration analgesia versus patients who receive adductor canal block and local infiltration.

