#### Primary and Secondary Study Endpoints

Primary objective: Compare the rate of IV opioid consumption in patients who receive a combination of adductor canal block, obturator nerve block, and local infiltration analgesia at the surgical site versus patients who receive adductor canal block and local infiltration analgesia.

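### The SAP gives no rule for patients who never reach breakthrough pain or ambulation while observed, and its only test that fits a time, the t-test, has no value to enter for them

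*SAP*

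**What the plan says.** The protocol lists two times to an event among its five secondary objectives, once at the start and again under Primary and Secondary Study Endpoints: "Compare time to breakthrough pain after surgery in patients who receive adductor canal block" and "Measure time to ambulation in patients who receive adductor canal block".

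The SAP is a single paragraph. Categorical variables get a chi-square or Fisher's exact test, binary outcomes get odds ratios with 95% confidence intervals, and for the rest "For continuous variables, independent t-test was used". It names no time-to-event method and no rule for a patient without the event. No other text available for this review supplies either.

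How long patients are observed for these events cannot be read from that text. Pain at rest is scored at 1, 6, 12 and 24 hours, but Description of the Study Design also says "You will periodically be asked questions regarding your pain and nausea and vomiting during the rest of your hospital stay". The data collection sheet takes items from the "first completed physical therapy session, including total distance ambulated, pain at time of assessment", and "Post-discharge data to be collected include total dosage of narcotics used after discharge, pain score, and any complications".

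**The concern.** A patient with no breakthrough pain by the end of observation has no time to breakthrough pain, and a patient who has not yet walked has no time to ambulation. A t-test cannot use a patient without a value. The analyst must therefore drop the patient, assign the window end, or leave the t-test for another method. The SAP leaves that choice open, so it could be made after the data are seen.

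Dropping is the harmful option. For breakthrough pain, the patients removed are those with the best analgesic result. For ambulation, they are those with the worst mobility result. In both cases they are removed because of their outcome, so randomisation no longer protects the comparison.

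The ambulation endpoint has a specific job. The protocol's Background cites a result that an obturator block added to a femoral triangle block did not impair ambulation, and states a belief that the same holds for the combination studied here. Time to ambulation tests that belief. Dropping non-walkers would hide part of a delay if there is one, or part of a benefit.

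**Working it through.** The documents give no sample size, event rate, median or window for these endpoints, so there is no stated figure to reproduce. Every input below is an assumption, chosen to show size.

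**Formulas.** For exponential times with median m, the rate is λ = ln 2 / m. With window τ:
- event-free share S = exp(−λτ)
- mean time counted to the window end (restricted mean) = (1 − S)/λ
- mean among patients with the event only = 1/λ − τS/(1 − S)

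**Breakthrough pain, medians 12 and 24 h, window 24 h.**
- Median 12 h: 1/λ = 17.31 h and S = 0.25. Restricted mean = 0.75 × 17.31 = 12.98 h. Events only = 17.31 − 24 × 0.25/0.75 = 9.31 h.
- Median 24 h: 1/λ = 34.62 h and S = 0.50. Restricted mean = 0.50 × 34.62 = 17.31 h. Events only = 34.62 − 24 × 0.50/0.50 = 10.62 h.
- True restricted-mean difference: 17.31 − 12.98 = 4.33 h. Events only: 10.62 − 9.31 = 1.31 h, or 30% of it.

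**Share of the true difference left when event-free patients are dropped** (median ratio 1.5 to 2). It does not depend on sample size or on the window in hours.

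| Event-free in slower arm | Share left |
|---|---|
| 2% | 84-88% |
| 5% | 72-78% |
| 10% | 60-66% |
| 20% | 46-52% |
| 50% | 28-30% |

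**Power** by simulation: 4000 replicates, 50 per arm, two-sided 0.05, everyone followed to the window end.

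| Scenario (medians; window) | Difference, events only / true | t-test, events only | t-test, event-free set to window end | Log-rank |
|---|---|---|---|---|
| Breakthrough pain, 12 vs 24 h; 24 h | 1.3 / 4.3 h | 11% | 71% | 78% |
| Ambulation, 8 and 12 h; 24 h | 1.2 / 2.9 h | 14% | 41% | 44% |
| Ambulation, 8 and 12 h; 72 h | 4.8 / 5.5 h | 44% | 51% | 52% |

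In the ambulation rows, 12.5% and 25% have not walked by 24 h, and 0.2% and 1.6% by 72 h.

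**No true effect** (12 vs 12 h, 24 h window): the three tests rejected 5.1%, 4.8% and 4.6% of the time.

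**Can the sign change?** One hand-built case shows that it can. Control: 50% at 4 h and 50% at 16 h, mean 10.0 h. Block: 50% at 4 h, 20% at 16 h and 30% event-free at 24 h. Events only, the block mean is (0.5 × 4 + 0.2 × 16)/0.7 = 7.4 h, a difference of −2.6 h. Counting event-free patients to 24 h, it is 2.0 + 3.2 + 7.2 = 12.4 h, a difference of +2.4 h. This shows possibility, not likelihood.

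**The case against.** The strongest reply is that the SAP never says event-free patients will be dropped. A reader might infer that it does, or that it assigns the t-test to these two endpoints by name; it does neither. The t-test follows only from the general rule for continuous variables, and no other listed test fits a time that has not been dichotomised. If event-free patients were set to the window end, power in the breakthrough pain example would be 71% against 78% for log-rank, and 41% against 44% for ambulation at 24 h. Exponential times also give proportional hazards, the case that favours log-rank most. This part of the objection stands: a t-test is not in itself the main fault.

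Second, event-free patients may be rare, especially for ambulation. Planning to record the distance walked at the first completed therapy session suggests, without proving, that most patients are expected to walk during the stay. No text sets a 24 h limit for ambulation; that figure belongs to the rest-pain scores. With a 72 h window the assumed loss is small. This stands too, and makes the ambulation half conditional.

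Third, a reader might infer that the protocol fails to define the events or the window. Parts of the protocol were not in the text available for review and could hold both, so that is not claimed. What remains is that the SAP's own paragraph has no handling rule.

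**Conclusion.** The point holds as a should-fix gap in the SAP. Two of the five secondary objectives are times to an event, and the plan does not say how patients without the event enter the comparison. If they are dropped, the estimate is distorted by an amount that depends on the event-free share: about a quarter of the true difference is lost at 5% in the slower arm, about half at 20% and about 70% at 50%, under exponential times with a median ratio of 1.5 to 2. If nearly all patients have the event, the bias is small or absent.

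Three stronger readings are not supported:
- Inflated false positives: rejection stayed near 5% in the null scenario run.
- A likely reversal of the result: this was shown only in one constructed example, and every simulated scenario with an effect gave attenuation or, at most, no visible difference.
- Harm to the main result: the primary opioid comparison does not use these times.

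The concern is stronger for breakthrough pain, which a good block may prevent altogether during observation, than for ambulation.

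**What to change.** In the SAP, limit the t-test to outcomes that have a value for every patient, and add one paragraph on the two time endpoints.

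**Minimum.** Use one fixed window in both arms, within the period observed for nearly all patients. Keep all randomised patients, count event-free patients to the window end, and report the number event-free per arm. Every patient followed to the window end then has a value, and a t-test on it compares restricted means. This removes most of the harm.

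**Preferred.** Analyse both endpoints with Kaplan-Meier curves and a log-rank test, with a restricted mean time difference or hazard ratio and its 95% confidence interval, censoring event-free patients at the window end. Report how many were censored earlier. Because discharge may depend on pain or walking, add a simple sensitivity analysis for patients discharged event-free before the window end, counting them once as event-free to the window end and once as events at discharge.

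**Fallback.** If breakthrough pain is known only from the scheduled scores, or event times cannot be recovered, compare the proportion with the event by the window end, using the chi-square or Fisher test and odds ratio already in the SAP.

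**Cost.** A little more analysis with standard SAS procedures, using records already planned as the source ("Relevant preoperative, intraoperative, and postoperative data will be obtained from the anesthesia record, the EPIC electronic medical record") where they hold the times. No new patients are needed, and no added follow-up if the window lies within the observed period. The SAP is written in the past tense; if results already exist, label this a re-analysis.
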